## 2. Introduction

Both dipeptidyl peptidase-4 (DPP-4) inhibition and sodium glucose-cotransporter-2 inhibition (SGLT2-) are glucose-lowering strategies in type 2 diabetes, although with different mechanisms of action. Thus, DPP-4 inhibition works mainly on the islets to stimulate insulin secretion and inhibit glucagon secretion (1) whereas SGLT-2 inhibitors work mainly on the kidney to facilitate glucose excretion (2). A main indication of these two treatment strategies is as add-on to metformin in subjects with inadequate glycemic control when given metformin in monotherapy.

A potentially important differentiation between the therapies is their different actions on alpha-cell function. Thus, DPP-4 inhibition, as we have shown with vildagliptin, is

known to inhibit glucagon response to mixed meal ingestion and this inhibition is associated with the improved glycemia (3). In contrast, treatment with SGLT-2 inhibition has been shown to increase glucagon secretion which increases liver glucose production (4). This effect of SGLT-2 inhibition may be an adaptative response to the increased glucose excretion which may counteract a glucose-lowering action. It thus seems that the two approaches of reducing glucose have opposite effects on a key factor underlying type 2 diabetes, the augmented glucagon response. However, it is not known to what degree glucagon secretion is differently regulated by DPP-4 inhibition versus SGLT-2 inhibition in the clinical context as add-on to metformin and it is also not known to what degree a differentiation on glucagon secretion affects glucose homeostasis. One reason for this lack of knowledge is that this has not been tested in head-to-head-studies. Such information is important when designing the most appropriate pathophysiological treatment of the disease.

Therefore, in this study, the DPP-4 inhibitor vildagliptin or the SGLT-2 inhibitor dapagliflozin will be added to metformin in subjects treated with metformin as monotherapy and their respective effects on meal-induced glucagon secretion will be evaluated.

### **3. Objective of the study**

To assess if vildagliptin and dapagliflozin have dissociated effects on glucagon secretion after a mixed meal ingestion in metformin-treated subjects with type 2 diabetes and whether this is associated with effects on glucose homeostas

[figure not shown]
### **4. Study design**

The study will be carried out according to this protocol and in compliance with the Declaration of Helsinki and applicable Swedish laws and regulations. This is an open label cross-over study. Twenty-eight patients with metformin-treated type 2 diabetes and HbA1c 43-72 mmol/mol (6.0-9.0%) will be randomized. Each patient will attend one

screening visit (Week -4) where the inclusion/exclusion criteria will be assessed. Eligible patients will then be randomized at visit 2 (Day 1) and complete two treatment periods, receiving a different study medication during each period (vildagliptin 50 mg BID and dapaglizlozin 10 mg QD, in random order) in addition to their continued metformin regimen. A baseline visit will be performed during each of the two treatment periods, at which the patient will be assessed and the study medication will be dispensed for two weeks of outpatient treatment. After two weeks of treatment, a mixed meal will be served. The standardized mixed meal must, which will be consumed in 15 minutes, consists of 524 kcal as rye and wheat bread (67% carbohydrate; 60g), 40% enriched margarine (10g), smoked ham from pork with 3% fat (15g), cheese with 17% fat (15g), juice (285g), green paprika (40g), light sour milk with 0.5% fat (200g) and mix-muesli cereal with fruit (40g) with water and non-sweetened decaffeinated coffee/tea. The meal consists of 524 kcal with 60% from carbohydrate, 20% from fat and 20% from protein.

The study medication will then be discontinued and a four-week washout period will occur before the next two week treatment period is started. This two-week treatment period will end with ingestion of a mixed meal, as after the first treatment period.

## Figure of Study Design

Each patient will therefore receive two treatments in a randomized design:

Vildagliptin 50 mg twice daily (BID) during weeks 0-2 and Dapagliflozin 10 mg once daily (QD) during weeks 6-8 or

Dapagliflozin 10 mg QD during weeks 0-2 and Vildagliptin 50 mg BID during weeks 6-8

The study medication will not be blinded.

## 5. Study population

The study population will consist of male and female patients with metformin-treated type 2 diabetes and HbA1c 6.0-9.0% (inclusive) (43-72 mmol/mol; inclusive), aged 20-75 years. It is planned to screen approximately 56 patients in order to randomize 28.

### 5a. Inclusion criteria

1. Written consent has been given.
2. Patients with type 2 diabetes treated with a stable dose of metformin during the last three months
3. Age 20-75 years.
4. HbA1c 6.0-9.0% (43-72 mmol/mol) at visit 1.
5. Ability to complete the study

### 5b. Exclusion criteria:

1. Use of other glucose-lowering therapy than metformin within three months prior to visit 1.
2. A history of any secondary forms of diabetes, e.g., Cushing's syndrome and acromegaly.
3. Type 1 diabetes, positive GAD antibodies
4. eGFR  $\leq$  60 ml/min
5. Acute infections which may affect blood glucose control within 4 weeks prior to visit 1
6. Any history of recent (<2 weeks) recurrent or severe hypoglycemic episodes.
7. Any history of acute pancreatitis

8. Any history of anaphylaxis, angioedema, and exfoliative skin conditions including Stevens-Johnson syndrome.
9. Liver disease such as cirrhosis or chronic active hepatitis
10. History of coronary heart disease within preceding 6 months or heart failure class III or IV
11. Donation of one unit (500 ml) or more of blood, significant blood loss equaling to at least one unit of blood within the past 2 weeks or a blood transfusion within the past 8 weeks.
12. Treatment with growth hormone or chronic oral or parenteral corticosteroid treatment (> 7 consecutive days of treatment) within 8 weeks prior to visit 1.
13. Use of other investigational drugs at visit 1 or within 30 days of visit 1, unsuitable for the study
14. Hypersensitivity to vildagliptin or dapagliflozin or any compound in the tablet core

## 6. Study medication

### 6a. Study drug

The study drug vildagliptin is a DPP-4 inhibitor meaning that it inhibits the enzyme DPP-4. This enzyme is responsible for the inactivation of the incretin hormones (mainly GLP-1) and therefore the study drugs prevent the inactivation of these hormones. This in turn results in increased plasma levels of the active form of the incretin hormones which through effects on islet hormone secretion result in reduced fasting and postprandial glucose and therefore HbA1c in subjects with type 2 diabetes. Vildagliptin is a small molecule which is taken orally twice daily. In terms of adverse events, it has been shown to be safe in studies undertaken so far. The study drug was approved by EMA in 2008 and is a well-established glucose-lowering therapy in type 2 diabetes world-wide, including in Sweden.

The study drug dapagliflozin is a SGLT-2 inhibitor meaning that it inhibits the enzyme SGLT-2. This enzyme is responsible for reabsorbing glucose in the renal tubule and therefore to prevent glucosuria. Inhibition of this enzyme, therefore, inhibits glucose reabsorption which increases glucose excretion in the urine which in turn reduces circulating glucose in subjects with type 2 diabetes which results in lowering of HbA1c. Dapagliflozin is a small molecule which is taken orally once daily. In terms of adverse events, it has been shown to increase the risk of genital infections but apart from that to be safe in studies undertaken so far. The study drug was approved by EMA in 2012 and is now a well-established glucose-lowering therapy in type 2 diabetes world-wide, including in Sweden.

#### **6b. Handling of study medication.**

Vildagliptin and dapagliflozin are distributed to the Clinical Research Department from the Pharmacy at the University Hospital. Patients will be given a box with for vildagliptin 28 tablets à 50 mg which covers the 2 week treatment period at the dosage of BID. For dapagliflozin, patients will be given a box with 14 tablets à 10 mg which covers the 2 week treatment period at the dosage of QD. The boxes will be given to the patients at the Clinical Research Department by the Study Nurse. At randomization, subject will receive a written dosage card explaining the dosage of the study medications. After end of treatment period, remaining study medication will be destroyed by the hospital pharmacy.

### **7. Study flow and methods**

#### **7a. Study flow**

Visits are scheduled at Week -4, Day 1, Weeks 2, 6 and 8. On visit days patients should have fasted overnight (i.e. no food or drinks, except water, after 10 pm on the day prior to the scheduled visit). Study visits should occur before 10 am. Medication should not be taken the morning of study visits. Table 1 lists all of the assessments and indicates with an "X" the visits when they are performed.

**Table 1 Assessment schedule**

Visit	1	2	3	4	5
Week	-4	Day 1	2	6	8
Informed Consent	X				
Inclusion/exclusion criteria	X	X			
Record concomitant medications	X	X	X	X	X
Height	X				
Anti GAD/fasting C-peptide	X				
Demography, history of diabetes, medical history	X				
Urine pregnancy test (for premenopausal women)	X	X	X	X	X
Mixed meal test			X		X
Physical examination	X				
Vital signs, body weight	X	X	X	X	X
ECG,	X				X
Hematology, Liver enzymes, creatinine	X	X	X	X	X
HbA1c, fasting glucose	X	X	X	X	X
Adverse events including hypoglycemia			X	X	X

### 7b. Methods

A mixed meal will be ingested at Week 2 and Week 8 following. Patients will arrive at the study site in the morning after an overnight fast (from 10 pm). Patients should be instructed to bring their study medication to these visits. Study medication (vildagliptin or dapagliflozin) and the usual morning dose of metformin will be taken 15 minutes

before the start of the standardized mixed breakfast. The start of the meal will be designated time 0 (t = 0 min).

The standardized mixed breakfast meal must be consumed in 15 minutes, and will consist of 524 kcal as rye and wheat bread (67% carbohydrate; 60g), 40% enriched margarine (10g), smoked ham from pork with 3% fat (15g), cheese with 17% fat (15g), juice (285g), green paprika (40g), light sour milk with 0.5% fat (200g) and mix-muesli cereal with fruit (40g) with water and non-sweetened coffee or tea. This breakfast consists of 524 kcal with 60% from carbohydrate, 20% from fat and 20% from protein.

Sampling of blood for determination of plasma levels of glucose, glucagon, insulin, C-peptide, intact and total GLP-1, intact and total GIP will be performed at fixed time points as described in Table 2.

**Table 2. Sampling in the mixed meal test**

Time (min)	Procedures	Blood sample for analysis of hormones
-30		
-25		
-20		X
-15	Drug intake	
-10		
-5		X
0	Meal served	
5		X
10		X
15		X
20		
30		X

45		X
60		X
75		X
90		X
120		X
150		X
180		X
240		X

## 8. Randomization

Randomization list will be prepared by statistician at Region Skåne and study medication will be distributed to the patient according to the randomization. The study medication will not be blinded and all patients will receive both vildagliptin and dapagliflozin in a cross-over design. The randomization, therefore, is in which order the study medication will be taken.

## 9. Data management and safety registration

**Registration.** The data are recorded in case and visit notes (hospital records) and entered in the CRF containing demographic and medical information, laboratory data, electrocardiograms, and the specific study-related results of any other tests or assessments. Specific worksheets will be the source documents for the variables derived from the mixed meal test. These will be stored in the CRF. A certified study monitor will regularly inspect the CRFs to ensure accuracy with source data.

**Safety.** At first visit, study subjects are informed of the characteristic symptoms of acute pancreatitis (persistent and abdominal pain). Adverse events are acute pancreatitis and hypoglycemia and all other symptoms reflecting a change in the health situation reported by the participating subjects. Adverse events are sought by non-directive questioning of the patient at each visit during the study, except directive questioning of

symptoms of acute pancreatitis and hypoglycemia. Adverse events also may be detected when they are volunteered by the patient during or between visits or through physical examination, laboratory test, or other assessments. All adverse events, including hypoglycemias, are recorded in the clinical case note and CRF and classified as of mild, moderate or severe degree, and a judgment whether it is related or unrelated to study medication. Hypoglycemia is defined as either a)symptomatic hypoglycemia, b)confirmed hypoglycemia (blood glucose  $\leq 3.1$  mmol/l) or c)hypoglycemia episode that require assistance for control.

The SmPC will be used for Reference Safety Information (RSI) for expected Serious Adverse Events (SAE). These are defined as any untoward medical occurrence that

- Results in death
- Is life threatening (which refers to an event/reaction in which the patient was at risk of death at the time of the event/reaction; it does not refer to an event/reaction which hypothetically might have caused death if it were more severe),
- Requires inpatient hospitalization or results in prolongation of existing hospitalization,
- Results in persistent or significant disability/incapacity, or
- Is a medically important event or reaction.

Medical and scientific judgment should be exercised in deciding whether other situations should be considered serious, such as important medical events that might not be immediately life-threatening or result in death or hospitalization, but might jeopardize the patient or might require intervention to prevent one of the other outcomes listed in the definition above.

The investigator informs the sponsor on an SAE within 24 hours and an AE within 7 days and the sponsor reports SAE to the sponsor within 24 hours.

DSUR (Development Safety Update Report) and Serious Unexpected Suspected Adverse Reaction (SUSAR) will be reported to the Medical Products Agency (through the EudraVigilance database) by the sponsor.

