## **15. Risk-benefit analysis**

This is a study aiming at understanding the glucagon response to a mixed meal ingestion after two weeks treatment with the DPP-4 inhibitor vildagliptin and the SGLT2-inhibitor dapagliflozin in patients with metformin-treated type 2 diabetes. Since the study is a mechanistic study, it is of no immediate benefit for the participating patients. The results of the study will, however, be beneficial for the patient group treated with this therapy since it will provide rationale for future treatment by allowing the most pathophysiological treatment to be prescribed to subjects with type 2 diabetes. The risk for the patients participating in the study is minimal since both drugs have been shown to be safe with low risk of adverse events, even in long-term studies, with the exception of genital infections with dapagliflozin. Furthermore, the risk with the mixed meal test is minimal in view of the extensive experience with this test at the Clinical Research Department.

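### Genital infection, the one risk the protocol names for dapagliflozin, is not among the events asked about directly and may be under-reported

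*Protocol*

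**What the plan says.** Protocol Section 9 sets the rule: "Adverse events are sought by non-directive questioning of the patient at each visit during the study". The same sentence then carves out two exceptions, which staff ask about by name: "symptoms of acute pancreatitis and hypoglycemia". It then adds two further routes: reports that patients volunteer at or between visits, and detection "or through physical examination, laboratory test, or other assessments". The definition of an adverse event is open, so any change in health that a patient reports counts, and all events go into the CRF.

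Section 6a says of dapagliflozin that "it has been shown to increase the risk of genital infections" and otherwise calls it safe. Section 15 describes the risk of both drugs as low, "with the exception of genital infections with dapagliflozin". Neither Section 9 nor Table 1 mentions genital infection.

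Table 1 places adverse-event recording at Visits 3, 4 and 5 (weeks 2, 6 and 8). It schedules the physical examination at Visit 1 only. Section 11 lists no safety end-point, and neither Section 13 nor the SAP describes an analysis of adverse events.

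**The concern.** The protocol already accepts that some events should be asked about by name. The two it chose are not attributed to either drug in Section 6a or Section 15, while the event that both sections do attribute to dapagliflozin is left to an open question. No reason is given. Patients may be slow to raise genital symptoms unless asked. That is a reasonable inference, not something the documents state.

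What is at stake is safety detection: an event could be noticed late or not recorded, in a study that Section 15 says brings participants no immediate benefit. The comparison of glucagon between the drugs is not at stake.

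**Working it through.** The plan states no figure on this point, so there is nothing to reproduce. The check is mainly a comparison of sections.

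**1. Questioning.** Section 9 has two directly solicited events, and genital infection is neither. It falls under the open question.

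**2. The other routes in Section 9, set against Table 1.**
- Physical examination: Visit 1 only, before any study drug.
- Laboratory tests during the study: hematology, liver enzymes, creatinine, HbA1c and fasting glucose. The only urine test is the pregnancy test.
- Other assessments after dosing starts: vital signs, body weight, ECG (Visit 5) and the mixed meal test. None is aimed at genital infection.

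So detection depends on the patient mentioning the symptom, either to the open question or unprompted.

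**3. Timing.** A patient who takes dapagliflozin first (weeks 0-2) is asked at Visit 3 and again at Visits 4 and 5. One who takes it second (weeks 6-8) has a single scheduled adverse-event visit after starting it, Visit 5, which is also the last visit.

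**4. Scale, for illustration only.** From the protocol: n = 28 patients, each planned to take dapagliflozin for 14 days. Assumed, because the documents give neither: p, the true two-week risk (1% to 10%), and s, the share of events reported under open questioning (25% to 100%).

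Expected cases = 28p. Chance of recording at least one = 1 − (1 − ps)^28.

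| Assumed p | Expected cases | Chance of ≥1 recorded, s = 100% | s = 50% | s = 25% |
|---|---|---|---|---|
| 1% | 0.28 | 24.5% | 13.1% | 6.8% |
| 3% | 0.84 | 57.4% | 34.5% | 19.0% |
| 5% | 1.4 | 76.2% | 50.8% | 29.7% |
| 10% | 2.8 | 94.8% | 76.2% | 50.8% |

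Expected unrecorded cases = 28p(1 − s). At p = 5% and s = 50% this is 28 × 0.05 × 0.5 = 0.7. The extreme of the ranges is 28 × 0.10 × 0.75 = 2.1, and at s = 100% the loss is zero.

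**5. What full ascertainment could achieve.** With no events in 28 patients, the one-sided 95% upper bound solves (1 − p)^28 = 0.05, so p = 1 − 0.05^(1/28) = 10.1%. With 24 completers it is 1 − 0.05^(1/24) = 11.7%. Direct questioning would not turn this study into a useful estimate of the rate.

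**The case against.** The strongest reply is that Section 9 does look for these events. Staff ask an open question at each visit, each treatment period ends with an adverse-event visit, volunteered reports are an additional route, and anything reported is recorded. All of this stands. A reader might infer that genital infection is left to spontaneous report, and the text does not support that.

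A reader might also infer that ascertainment differs between the drugs. The same questions apply in both periods and every patient is planned to take both drugs, so the difference is between types of event. What remains is that any under-reporting of this event would fall mainly on the count for dapagliflozin.

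It is tempting to say that the adverse-event table would understate a known risk. The documents describe no such table and no safety comparison.

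Nor can one conclude that patients are warned about pancreatitis alone. Section 9 says "At first visit, study subjects are informed of the characteristic symptoms of acute pancreatitis", but it does not say that nothing else is explained, and the consent pages were not available for this review.

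Two further arguments have some weight. The existing list has a logic: pancreatitis is the example given in the withdrawal criteria (Section 10), and hypoglycemia has a formal definition in Section 9. And in an open-label study, a prompt about one drug's known effect may inflate reports in that drug's period. The first does not explain why the named risk was left out. The second is a real but small cost, and the protocol already accepts direct questioning for two other events.

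**Conclusion.** The mismatch between Sections 6a and 15 on one side and Section 9 on the other is real, and Table 1 offers no planned on-treatment assessment that makes up for it. The conclusion is that genital infection may be under-reported. A reader might go further and say that it is under-ascertained, but no figure in the documents shows that any event would be missed.

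The size cannot be computed from the documents. Under the assumed ranges (risk 1% to 10%, reporting share 25% to 100%), the expected loss among 28 patients runs from none to about two cases. Importance is low: this is a mechanistic study with 14 days on each drug and no safety end-point, and the glucagon analysis does not change.

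**What to change.** In Section 9, add symptoms of genital infection to the events asked about directly. Ask with identical wording at Visits 3, 4 and 5, whichever drug the patient has taken, so that the prompt itself does not differ between periods.

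The cost is one question at each of three visits and one line each in the protocol and the CRF. No end-point, sample size or visit changes. More mild events will be recorded and, because patients and staff know the treatment, some prompted over-reporting in the dapagliflozin period is possible. Any report of adverse events should state that this event was directly solicited.

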## **10. Withdrawal criteria**

A subject may be withdrawn from the trial at the discretion of the Sponsor if judged non-compliant with trial procedures or due to a safety concern.

A subject must be withdrawn if the following applies:

1. **Withdrawal of consent:** The subject may withdraw at will at any time.
2. **Protocol deviation:** If a protocol violation or concurrent illness occurs, which, in the clinical judgement of the Sponsor, may invalidate the trial, the subject will be withdrawn by the Sponsor.
3. **Change in medication:** If a subject changes the dose of their existing medications during the trial, which, in the clinical judgement the Sponsor, may invalidate the trial, the subject will be withdrawn by the Sponsor.
4. **If a subject reports symptoms, which are considered unacceptable by the subject or the Sponsor, such as acute pancreatitis, the subject will be withdrawn from the trial.**

## **11. End-points**

**Primary end-point** is the effect on the area under the curve (AUC) of the 180 min glucagon levels after mixed meal ingestion

**Secondary end-points** are the effect on AUC180 of GLP-1, GIP, insulin, C-peptide and estimated ISR (insulin secretory rate).

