## **12. Sample size calculation**

The sample size calculation was based on detecting a difference between vildagliptin and dapagliflozin in the AUC of glucagon level during the 300 min after mixed meal ingestion after 2 weeks of treatment. Previous studies on the effect of vildagliptin (3) and dapagliflozin (4) showed a reduction of glucagon by vildagliptin and an increase of glucagon by dapagliflozin. Based on these data and expecting similar variation in the data in the population studied here, a power analysis aiming at showing a 30% difference in glucagon levels by the two drugs with 90% sensitivity results in requirement of 24 subjects when doing paired analysis. To allow for even more safe statistics and allow for discontinuation, we will recruit four additional subjects; hence we aim at including 28 patients in the study.

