### **13. Statistical evaluation**

The variables will be analyzed using a 2-sided paired test. The Completers population alone will be used.

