Statistical analysis plan Protocol 350A

Trial NCT02475070

Study of the Effect of Vildagliptin versus Dapagliflozin on Glucagon

Response to Mixed Meal in Metformin-treated Subjects with Type 2

Diabetes

Glucagon

Comparison between the two groups are performed with parametric t-test for glucagon in samples taken at -5, 15, 30, 45, 60, 90, 120, 180 and 240 min after meal ingestion and area under the 240 min curve (AUC) for glucagon

Insulin, C-peptide, GIP and GLP-1

Comparison between the two groups are performed with parametric t-test for insulin, C-peptide, intact and total GIP and GLP-1 samples taken at -5, 15, 30, 45, 60, 90, 120, 180 and 240 min after meal ingestion and area under the 240 min curve (AUC) for insulin, C-peptide, intact and total GIP and GLP-1.

Lund, March 28, 2016

[name], PI

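### The primary end-point is the 180 min glucagon AUC, the SAP analyses only a 240 min AUC, and the sample size rests on a 300 min AUC that the sampling schedule cannot supply.

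*Protocol*

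**What the plan says.** Three AUC windows appear for the same hormone.

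- **Protocol Section 11 (End-points): 180 min.** The primary end-point "is the effect on the area under the curve (AUC) of the 180 min glucagon levels after mixed meal ingestion". The secondary end-points (GLP-1, GIP, insulin, C-peptide and estimated insulin secretory rate) also use the 180 min AUC.
- **SAP: 240 min.** For glucagon it plans the "area under the 240 min curve (AUC) for glucagon", and for the other hormones the "area under the 240 min curve (AUC) for insulin, C-peptide, intact and total GIP and GLP-1". Beside the AUC it plans t-tests for "glucagon in samples taken at -5, 15, 30, 45, 60, 90, 120, 180 and 240 min after meal ingestion". No analysis is called primary.
- **Protocol Section 12 (Sample size calculation): 300 min.** The calculation concerns "the AUC of glucagon level during the 300 min after mixed meal ingestion". A 30% difference "with 90% sensitivity results in requirement of 24 subjects when doing paired analysis". Then: "To allow for even more safe statistics and allow for discontinuation, we will recruit four additional subjects", which makes 28.

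Section 13 adds: "The variables will be analyzed using a 2-sided paired test. The Completers population alone will be used". It gives no window. Table 2, which governs sampling under Section 7b, ends at 240 min, as does the SAP's list of times. Both documents are dated 28 March 2016, and neither says which takes precedence.

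**The concern.** A primary end-point and its planned analysis should be the same variable. Here an analyst who follows the SAP exactly reports a glucagon AUC that the protocol does not name, and never computes the one it does name. The secondary AUCs have the same mismatch, and the insulin secretory rate in Section 11 is absent from the SAP altogether.

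Two things are at stake. First, with 180 and 240 min both written down and no precedence rule, the plan does not exclude choosing a window after seeing both results. Nothing suggests that results had been seen: Section 17 places the analyses in Q2/2016, after the date on the documents. Second, the stated power refers to a 300 min AUC, which would need 60 min of extrapolation beyond the last sample (300 − 240). It cannot be shown to apply to either window that can be analysed.

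**Working it through.** **1. Which windows can be computed**

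| Source | AUC window | Computable with last sample at 240 min? |
|---|---|---|
| Protocol Section 11, primary and secondary | 180 min | Yes |
| SAP, all hormones | 240 min | Yes |
| Protocol Section 12, sample size | 300 min | No |

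The sampling grid is also open. Table 2 marks samples at −20, −5, 5, 10, 15, 30, 45, 60, 75, 90, 120, 150, 180 and 240 min, and none at 0 min. The SAP's list leaves out −20, 5, 10, 75 and 150 min. Neither document says which sample starts the AUC or whether it is total or incremental.

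**2. The plan's own figure**

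The stated inputs are a 30% difference, 90% power, a paired analysis and n = 24 (Section 12), with a two-sided test (Section 13). The SD of the paired difference and alpha are not given, so 24 cannot be reproduced forwards. I assumed alpha = 5% and solved backwards.

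Power = P(|T| > t₀.₉₇₅,ₙ₋₁), where T is noncentral t with n − 1 degrees of freedom and noncentrality d√n. Setting n = 24 and power = 0.90 gives d = 0.691, so the implied SD of the difference is 30/0.691 = 43.4%.

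**3. Power if the standardised difference in the analysed window differs**

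| Standardised difference | 24 completers | 28 completers |
|---|---|---|
| 0.8 × 0.691 = 0.553 | 73.7% | 80.5% |
| 0.691 (no change) | 90.0% | 94.1% |
| 1.2 × 0.691 = 0.829 | 97.3% | 98.8% |

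The 20% steps are illustrative. The documents do not indicate which direction applies.

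**4. Type I error if either AUC may be chosen after seeing both**

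This was simulated with 24 pairs, no treatment difference, two paired t-tests at two-sided 5%, and success if either is significant.

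| Correlation of the two AUC differences | Type I error |
|---|---|
| 0.99 | 5.7% |
| 0.95 | 6.5% |
| 0.90 | 7.1% |
| 0.85 | about 7.5% |

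To see which rows are realistic, I computed the correlation between the nested 180 and 240 min trapezoid AUCs, starting at −5 min, with equal variances and a common correlation between time points:

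| Between-time correlation | AUC correlation (Table 2 times; SAP times) |
|---|---|
| 0 | 0.85; 0.90 |
| 0.2 | 0.956; 0.963 |
| 0.5 | 0.986; 0.987 |
| 0.7 | 0.994; 0.994 |

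Under this model the 7.1% and 7.5% rows need a patient's values at different times to be uncorrelated. With a between-time correlation of 0.2 or more, type I error is about 6.5% or less.

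**5. Effect of the grid**

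Under the same model, the 180 min AUC on Table 2 times correlates with that on SAP times at 0.80, 0.93, 0.98 and 0.99 for between-time correlations of 0, 0.2, 0.5 and 0.7. The choice of grid is a smaller matter than the window, but it does change the variable.

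**The case against.** The best defence is that only one document names a primary end-point. Section 11 fixes it at 180 min, the SAP labels nothing primary, and Section 13 can be read as applying its paired test to the Section 11 variables. On that reading the SAP has omitted the primary end-point; it has not set up a rival. This is fair and narrows the room for choosing a window. It does not remove the defect, because the document meant to fix the analysis still plans a different AUC for every hormone and no rule says the protocol prevails.

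The numerical objections also carry weight. The higher type I figures depend on an unlikely correlation structure. The 20% power steps have no source in the documents, and if the 30% difference and its SD are the same in every window, power stays at 90%. The missing SD and alpha would prevent verification even if the windows agreed. So neither a loss of power nor a large error inflation can be claimed.

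On the grid, the SAP's times are attached to the single-time tests and need not define the AUC, and a −5 min sample can serve as the start. That makes the grid a point to specify, not a contradiction.

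Finally, with last-patient entry planned for April 2016, restating power will be mainly documentary. That limits what the recalculation can change, but it does not justify leaving the power claim on an unobservable window.

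**Conclusion.** The concern holds and must be fixed. Of the three stated windows, two can be computed and the one used for sizing cannot. Following the SAP as written would leave the protocol's primary end-point untested. This follows from the text alone and needs no assumption.

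The numerical consequences are conditional. The 90% power is unverified for 180 or 240 min, in an unknown direction. The power figures rest on an assumed two-sided 5% alpha and on illustrative shifts in the standardised difference. Post hoc choice between the two AUCs would inflate type I error only modestly. The severity comes from the unplanned primary end-point, not from that inflation. None of this shows that 24 or 28 is the wrong sample size.

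**What to change.** Before any treatment comparison is made:

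1. In the SAP, name the 180 min glucagon AUC as the single primary analysis. State the starting sample, the sampling times used, and whether the AUC is total or incremental.
2. Use 180 min for all secondary AUCs, including the insulin secretory rate, which the SAP does not now mention.
3. Keep the 240 min AUC as a named sensitivity analysis.
4. In Section 12, replace the 300 min basis with the 180 min AUC. Show the SD of the paired difference, alpha and the expected difference, and restate power for 24 completers, with 28 as the no-dropout case. Enrolment stays as planned; the restated figure documents what the sample can show.

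The cost is a short SAP edit and one recalculation from the data behind Section 12, with no new samples, visits or patients. The restated power may move either way, and the 180–240 min part of the response is then covered only by the sensitivity analysis.
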